Alternatively, we may mail recruitment letters and/or call patients who have participated in prior studies with this research team, or approach hospitalized dialysis patients at Duke.

Compensation:

Aim 1: Compensation for patients who consent to participate in the interview will be a gift valued at approximately \$30, or a check in the amount of \$30. Providers will be compensated with a \$75 gift card, and light refreshments will be provided at the focus group sessions.

Aim 2: Compensation for patients who complete the GOLD surveys **only** will be either a gift valued at approximately \$30, or a check in the amount of \$30. Patients who enroll to participate in an interview will be compensated with either a gift valued at approximately \$30, or a check in the amount of \$30. Patients who complete both the GOLD surveys and the interview will be compensated with either a \$60 check, or gifts with a total value of \$60, or a combination of a \$30 check and a gift valued at \$30 for completion of both portions of their study participation.

Patients will receive a gift valued at \$20 or a check for \$20 for completing the 3-month follow-up surveys.

Subject's Capacity to Give Legally Effective Consent

- If subjects who do not have the capacity to give legally effective consent are included, describe how diminished capacity will be assessed. Will a periodic reassessment occur? If so, when? Will the subject be consented if the decisional capacity improves?

Aim 1-

Providers and dialysis staff will be considered to be capable of consent by virtue of employment status (staff). Periodic reassessment will not occur.

Patients:

We plan to exclude patients with advanced dementia; therefore, potential subjects for this study are not expected to have diminished decision making capacity. If a potential subject does not appear to comprehend the study and its minimal risk during the informed consent process, we will assess for diminished capacity. This capacity determination will involve asking potential subjects to describe in their own words what the purpose, procedures, and/or risk of the study. If a potential subject is not able to restate the primary study procedures and risks, we will exclude the patient.

Study Interventions

- If not already presented in #4 above, describe study-related treatment or use of an investigational drug or biologic (with dosages), or device, or use of another form of intervention (i.e., either physical procedures or manipulation of the subject or the subject's environment) for research purposes.

This is a descriptive study with no study intervention

PI Attestation Statement Regarding DaVita's Engagement in Research

According to the protocol, DaVita staff (e.g., social worker, nurse, dietician, physician, advanced practice practitioner or technician) will only perform the following activities:

1. **Identify potentially eligible subjects and provide the study team the following list of information to facilitate eligibility screening:**
 - a. Patient's name and age
 - b. Location of patient's hemodialysis clinic
 - c. Patient's HD treatment schedule
 - d. Date of first HD treatment
2. **Present recruitment letter to eligible patients that describes the study and provides patients with information about study participation.**
 - a. Patients may indicate to DaVita staff if they would like to be contacted by study staff or not. This information will be shared with study staff, who will only contact those patients who have agreed.
 - b. Patients may also contact study staff themselves using the contact information provided in the recruitment letter.
 - c. Patients will be instructed by DaVita to contact the study staff if they have any questions about study participation.
 - d. Patients may choose to meet with study staff at DaVita sites to discuss enrollment but DaVita staff will not participate in the consent process in any way.
3. **Print patient information from electronic medical record for patients who meet with study staff and agree to participate by signing the informed consent form.**
 - a. Medication history
 - b. Medical history

"The activities listed above are considered part of DaVita's usual scope of practice, and therefore, as the PI for this study, I conclude that DaVita is not engaged in research activity and, therefore, does not require IRB oversight/approval."

Risk/Benefit Assessment

- Include a thorough description of how risks and discomforts will be minimized (per 45 CFR 46.111(a) (1 and 2)). Consider physical, psychological, legal, economic and social risks as applicable. If vulnerable populations are to be included (such as children, pregnant individuals, imprisoned persons or cognitively impaired adults), what special precautions will be used to minimize risks to these subjects? Also identify what available alternatives the person has if he/she chooses not to participate in the study. Describe the possible benefits to the subject. What is the importance of the knowledge expected to result from the research?

Potential Risks:

Aim 1: This aim involves subject interviews, and there is minimal psychological risk as the topic is not likely to be deemed sensitive by the subjects. There is a low risk of loss of confidentiality. Every effort will be made to minimize this risk by de-identifying data obtained from subjects and by assigning a study ID number as a subject identifier.

Aim 2: Subjects who have medications deprescribed (reduced dose or discontinued) as part of this deprescribing clinical program have potential risk of harm consistent with routine clinical care, including a low risk of adverse drug withdrawal events (ADWE). ADWE involve clinical signs and symptoms after medication removal or reduced dose, such as rebound hypertension or anxiety, and will be monitored for as per routine clinical practice. The research activities described herein (surveys and interviews) have similar minimal risk as described above for Aim 1.

For both aims: there is a minimal risk of loss of confidentiality from primary data collection (including interview transcripts) in the dialysis unit. Data from each subject will be imported directly to a secure folder behind the Duke network's firewall. Only key study personnel will have access to the data.

We will minimize risks and discomforts through the following activities:

1. data storage in a secure server in a confidential folder that is accessible only by study personnel
2. voluntary informed consent process
3. research procedures that will not interfere with or delay patient care in the dialysis unit

If potential subjects refuse to participate in the study, he/she will continue standard of care provided by dialysis providers. Because there is not an intervention for the study, the alternative therapy is to continue usual care provided by the patient's providers. The study will not include vulnerable populations.

Potential benefits of research to subjects and others: This research will reveal the most acceptable approach to deprescribing PIMs in older dialysis patients.

Importance of knowledge to be gained: Knowledge gained through this study is valuable for design of a clinical trial that targets deprescribing PIMs in older dialysis patients. PIMs are potentially modifiable risk factors for geriatric syndromes, hospitalizations, quality of life in older dialysis patients. The benefits of establishing evidence that improves health in these patients outweigh the potential risk.

Costs to the Subject

- Describe and justify any costs that the subject will incur as a result of participation; ordinarily, subjects should not be expected to pay for research without receiving direct benefit.

Study participants may incur travel costs for participation in a focus group or interview.

Data Analysis & Statistical Considerations

- Describe endpoints and power calculations. Provide a detailed description of how study data will be analyzed, including statistical methods used, and how ineligible subjects will be handled and which subjects will be included for analysis. Include planned sample size justification. Provide estimated time to target accrual and accrual rate. Describe interim analysis including plans to stop accrual during monitoring. Phase I studies, include dose escalation schema and criteria for dose escalation with definition of MTD and DLT.

Qualitative analyses will start with Rapid assessment. Rapid assessment involves team-based inquiry for triangulation, iterative data analysis, and data collection. This process allows data analysis before completion of data collection to facilitate rapid identification of key issues that inform intervention development. Subsequently, we will perform traditional qualitative analyses using ATLAS.ti software to summarize themes using framework analysis. Framework analysis will proceed in five steps by a team consisting of at least two study team members. This thematic framework will be refined through interim analyses of interview data until there is theme saturation. I anticipate theme saturation for each stakeholder group will practically be achieved after 2-3 focus groups of each provider type and 10-12 patient interviews.

Descriptive statistics will be performed to describe the patient participants' demographics and clinical characteristics and provider characteristics (role, experience, and for PCP participants, quantity of dialysis patients in clinical practice).

Aim 2 - We will perform descriptive statistics on the feasibility measures described under (Design and Procedures/Data collection for Aim 2), subject characteristics, survey responses, and types of PIMs prescribed. We will calculate intraclass correlations and standard errors to inform sample size for a clinical trial. We will also conduct a qualitative analysis from semi-structured interviews as described above.

Data & Safety Monitoring

- Summarize safety concerns, and describe the methods to monitor research subjects and their data to ensure their safety, including who will monitor the data, and the frequency of such monitoring. If a data monitoring committee will be used, describe its operation, including stopping rules and frequency of review, and if it is independent of the sponsor (per 45 CFR 46.111(a) (6)).

1. Data & Safety Monitoring:

Adverse drug withdrawal events (ADWEs) are the primary safety concern in the deprescribing Quality Improvement program we are evaluating in Aim 2. ADWEs include a physiological withdrawal reaction or intolerance of deprescribing (worsened symptoms). However, this risk is consistent with risk involved with routine clinical care. Still, we recognize the need to have a plan for safety monitoring that is outlined below:

- The deprescribing recommendation will provide providers and patients specific information on potential symptoms that may develop and contact information to the deprescribing clinical program if intolerance develops.
- If a patient experiences intolerance (worsened symptoms), they will have instructions based on an evidence-based protocol (e.g., adjust or stop the taper or seek immediate medical attention) and to contact the deprescribing team. Such a protocol will be specific to each target PIM for the pilot study. These protocols will be developed prior to study initiation and approved by a team of physicians and pharmacists. Medications can be restarted or increased at any time should patient not tolerate deprescribing.
- We will monitor for ADWEs after a month of deprescribing onset by reviewing electronic medical records for documentation of clinical event (e.g., unscheduled visit for a symptom or sign related to deprescribing of the target PIM). We will also communicate with each patient at this point. This communication will assess 1) if patient is tolerating the deprescribing plan and 2) if patient has experienced an adverse drug withdrawal events (ADWEs). Prior to that, patients who have concerns during deprescribing can reach deprescribing team. In that communication, the team will ask specific questions to inquire about ADWEs.
- As part of the clinical program, ADWEs will be immediately reviewed by team geriatric nephrologist ([name]) for immediate management recommendations; serious ADWEs will be communicated to the dialysis provider and/or PCP within 2 business days. We will encourage documentation in the patient's medical record.
- The PI (or designee) will report ADWEs that constitute SAEs to the Duke University IRB within 24 hours of learning about the event. Within 5 business days following the initial report, a Notification of a Problem or Event Requiring Prompt Reporting Form to the Duke IRB. The PI will also report SAEs to the NIA Safety Officer according to their reporting policies (if indicated).

- [REDACTED], a geriatrician who is not associated with the program, will serve as Safety Monitor. ADWEs will be reviewed with him quarterly. We will adjust the protocol if needed.

Additional concerns are Loss of Protected Health Information: The study team has outlined procedures for data management to protect against loss of data (detailed below). Breaches in data security will be reported within 24 hours of detection, and a plan for management of the breach and modification of data security procedures will be developed within 3 business days, if applicable.

Additional Oversight and Reporting: The PI, [name], will be responsible for the operation of this research study according to the study's protocol and IRB policies. In addition to adverse events described above, The PI (or designee) will submit complaints, withdrawals, and protocol violations to the Duke University IRB.

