Decision-making	The nephrologist decides whether to proceed with the recommendation and talk with the patient on their own. Research activity: Questions to nephrologist about acceptability of the recommendation (see text)	If approval from nephrologist, study team talks to patient about recommendation and that nephrologist supports the recommendation. education to patient about medication risk and process for deprescribing. Team asks if patient is willing to proceed with deprescribing
Deprescribing	If patient agrees, Nephrologist will provide instructions for deprescribing. Research activity: Questions to nephrologist about acceptability of the recommendation (see text) and deprescribing attempts Research activity: After a patient decides (either for or against deprescribing), they will be approached for consent for an interview and/or survey. This approach will be by recruitment letter mailed and/or provided in person at the dialysis clinic. We will document deprescribing in medical record and to pharmacy.	If patient agrees, the deprescribing team will provide instructions for deprescribing. Research activity: After a patient decides (either for or against deprescribing), they will be approached for consent for an interview. This approach will be by recruitment letter mailed and/or provided in person at the dialysis clinic. We will document deprescribing in medical record and to pharmacy.
Monitoring	Deprescribing team will assist patient with any issues during deprescribing step AND contact patient after a month to check on progress and ask about symptoms.	Deprescribing team will assist patient with any issues during deprescribing step AND contact patient after a month to check on progress and ask about symptoms.

Aim 2 Data collection: We are collecting data for program evaluation. we will assess demand, deprescribing attempts, change in PIM burden (number of PIMs) and feasibility (acceptability and practicality),

Demand: We will assess demand from chart review and define demand as the proportion of patients with a specific PIM divided by all patients with PIMs.

Deprescribing Attempts: We will assess number (and %) of deprescribing attempts in each format of the QIP. The denominator would be total number of patients who were approached for deprescribing decision-making. The approach for each format:

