- QIP – Provider Communication Only: We will ask dialysis providers if the patient agreed to deprescribe after a month.
- QIP – Provider / Patient Communication: We will collect information from the deprescribing team on whether the patient agreed to deprescribe.

participants who agreed to deprescribed were called after 3 months to see if they remained off PIM or at a lower dose of the PIM

Change in PIM burden: We will assess change in PIM burden as measured by Sustainability at 3 months; of those who can be reached, proportion of patients who remain off PIM at at a lower dose at 3 months. Participants who agree to deprescribe will be called after 3 months to see if they remain off PIM or at a lower dose of the PIM.

Time frame: 3 months.

Provider Acceptability: For the QIP-Provider Communication only format, we want to assess provider acceptability of the QIP recommendation. Specifically, When the nephrologist (or other dialysis provider) receives the recommendation from the deprescribing team, they will receive a short survey with two primary questions: 1) Will you implement this deprescribing plan? 2) If not, would you support implementation of this deprescribing plan if you had assistance from the deprescribing team? At the end of the month, we will ask the nephrologist some questions about the deprescribing plan: What worked about the deprescribing program recommendation? What did not work?

Patient acceptability: In both formats, we will assess patient acceptability. After a patient decides (either for or against deprescribing), they will receive a recruitment letter (either mailed to them, or given to them by a member of their care team) or may be called or approached in-person at the dialysis clinic to invite them to participate in an interview and a set of surveys. Patients will be able to choose to participate in data collection alone (baseline surveys and again at 3 months), or complete both an interview and the surveys. The consent process and interview will either be by phone or in person at the dialysis clinic. A description of the logistics for interviews is as described for Aim 1. The interviews will be audio recorded and later transcribed by an experienced transcriptionist. We expect to conduct interviews in 12-15 subjects. The focus of the interviews will be on acceptability of the clinical program (e.g., experience, perceived burden, negative consequences or side effects).

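### Deprescribing attempts are scored on reported patient agreement, from a different informant and time point in each format, so the percentages do not measure starts and are not comparable between formats

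*Combined protocol and SAP*

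**What the plan says.** In Design & Procedures, under Aim 2 Data collection, the outcome is named and its denominator given: "We will assess number (and %) of deprescribing attempts in each format of the QIP" and "The denominator would be total number of patients who were approached for deprescribing decision-making". The numerator rule follows, by format.

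- Provider Communication Only: "We will ask dialysis providers if the patient agreed to deprescribe after a month".
- Provider/Patient Communication: "We will collect information from the deprescribing team on whether the patient agreed to deprescribe". No time point is stated.

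The table of deprescribing steps earlier in the same section separates the decision from the act. In the decision-making row of the Provider/Patient format, "Team asks if patient is willing to proceed with deprescribing". The next row is the deprescribing step: "If patient agrees, Nephrologist will provide instructions for deprescribing" in one format and "If patient agrees, the deprescribing team will provide instructions for deprescribing" in the other. In both formats that row ends with "We will document deprescribing in medical record and to pharmacy", and the monitoring row adds a patient contact after a month. Risk/Benefit Assessment explains deprescribed as a reduced dose or a discontinuation.

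The change in PIM burden is measured at 3 months by calling those who agreed. The reported proportion is of those reached who are still off the drug or on a lower dose. Data Analysis & Statistical Considerations plans descriptive statistics for these measures.

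**The concern.** The label describes an act, and the rule counts a decision that comes before it. A patient who agrees but receives no instructions, or never changes the dose, is scored as an attempt. Neither the chart and pharmacy documentation nor the one-month contact is tied to the numerator. The table mentions questions to the nephrologist about attempts in Provider Communication Only, but gives no other definition.

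The informant and the timing also differ. One format relies on a provider asked after a month. The other relies on the team's account of a conversation it led itself. The plan sets out to evaluate the program with and without team help in decision-making, so the two percentages will be read side by side. A difference between them could come from the program, from follow-through after agreement, or from reporting, and the rule cannot separate these.

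The 3-month measure starts from the same group. It asks agreers whether they have stayed off or lower, which presumes that they started.

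The plan also intends to compute intraclass correlations and standard errors to size a later trial, without saying for which measures. If attempts are among them, that input would describe willingness.

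**Working it through.** The documents state no attempt rate, target or sample-size calculation for this outcome, so there is no figure to reproduce. The check compares definitions, then shows arithmetic on assumed values.

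**1. The rule, side by side**

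| | Provider Communication Only | Provider/Patient Communication |
|---|---|---|
| Event scored | patient agreed | patient agreed |
| Informant | dialysis provider | deprescribing team |
| When | asked after a month | not stated |
| Next step after agreement | nephrologist gives instructions | team gives instructions |
| Chart and pharmacy documentation | present, not linked to the count | present, not linked to the count |
| One-month patient contact | present, not linked to the count | present, not linked to the count |

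**2. Agreement against start.** Let A be the share of approached patients who agree and f the share of agreers who start. Then starts = A × f, the ratio of agreement to starts is 1/f, and the gap is A × (1 − f).

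- A = 0.60, f = 0.80: starts 0.60 × 0.80 = 48% against 60% by agreement; gap 12 points; ratio 1/0.80 = 1.25.
- A from 0.40 to 0.80, f from 0.60 to 1.00: gap from 0 to 0.80 × 0.40 = 32 points; ratio from 1.00 to 1/0.60 = 1.67.

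**3. Provider under-reporting.** Let s be the share of true agreements that the provider reports. Recorded attempts relative to true starts = s/f.

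- s = 0.80, f = 0.90: 0.80/0.90 = 0.89, an undercount.
- s = 0.90, f = 0.80: 0.90/0.80 = 1.125, an overcount.

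So in that format the direction is not fixed.

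**4. Between formats.** Suppose 50% truly start in both formats and agreement is recorded perfectly. With f = 0.90 in Provider Communication Only and 0.80 in Provider/Patient Communication, the reported figures are 0.50/0.90 = 55.6% and 0.50/0.80 = 62.5%. That is a difference of 6.9 points with no true difference in starts. Exchanging the two values of f reverses its sign.

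**5. The 3-month measure.** Take an assumed 30 patients approached (not the Aim 2 recruitment cap, which concerns interviews and surveys), of whom 20 agree, 15 start and 12 are off or lower at 3 months, all reached.

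- Among agreers: 12/20 = 60%. Among starters: 12/15 = 80%.
- End to end: 20/30 × 12/20 = 12/30 = 40%, and 15/30 × 12/15 = 12/30 = 40%.

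The 8 agreers who are not off or lower are 5 who never started and 3 who did not sustain. The rule cannot tell them apart, but the end-to-end result is the same.

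**6. The unreached.** If 85% of agreers are reached and 70% of those are off or lower, the proportion over all agreers lies between 0.85 × 0.70 = 59.5% and 59.5% + 15% = 74.5%.

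**The case against.** The best defence is that agreement suits the question. The formats differ in who leads decision-making, and the denominator is patients approached for a decision, so a decision numerator is coherent and openly stated. On this view the fault is mainly a loose label. That stands as a reason to keep agreement as a measure in its own right. It does not make agreement a measure of attempts.

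The differing informant follows partly from the formats: in Provider Communication Only the team takes no part in the decision conversation. That is fair, but it does not explain the unequal timing, and a common source for starts exists in both formats.

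The data needed are largely there already, through chart and pharmacy documentation, the one-month contact and the 3-month call. This narrows the problem to definition and reporting. A chart or pharmacy entry alone may record only the plan, so a documentation-based count needs confirmation from the patient.

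A reader might infer that the plan overstates what the program achieved. The documents do not support that: every agreer might start, under-reporting could push the provider-led count down, and the 3-month measure does not count a non-starter as a success. Nor do they rank attempts as the main outcome, or say that agreement is only verbal.

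**Conclusion.** The concern holds as a matter of definition and comparability. The attempt percentage is reported agreement, and its informant and timing differ by format. When recorded correctly it is an upper bound on starts, given that instructions follow agreement. With provider under-reporting, the Provider Communication Only count could fall below true starts. The per-format percentages are therefore not comparable as measures of deprescribing begun.

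No size can be derived from the documents. The figures above rest entirely on assumed follow-through, reporting and reach, and the gap may be zero. The 3-month proportion mixes two kinds of failure and leaves out the unreached, but the use of agreers as its base does not inflate end-to-end success.

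No test, threshold or power statement depends on this outcome, so no error rate is affected. What is affected is how the descriptive percentages are read, and possibly what is carried into a later trial. Format is allocated by staff availability, so better measurement would still leave a descriptive, non-randomised comparison.

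**What to change.** In each format, report two measures over the same denominator, all patients approached:

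1. **Patient agreed**, within one month in both formats, with the informant named.
2. **Deprescribing started**, meaning a dated reduction or discontinuation of the target PIM, documented in the medical record or to the pharmacy and confirmed at the existing one-month patient contact. Use the same source and the same one-month window in both formats, and state the event from which the month runs. Abstract the records for every patient approached, not only those reported as agreeing, so that provider under-reporting does not carry over into this measure.

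Report 3-month status among all agreers, with the number unreached shown, and also among those with a confirmed start. If attempts feed the intraclass correlations, say which of the two measures is used.

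The cost is protocol wording and one dated abstraction field. The work may be somewhat more where the dialysis unit keeps a separate record. The attempt percentage may be lower. The change concerns measurement only and leaves clinical management as it is.

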- We will not administer the chair stand test during COVID-19 restrictions.
- After the physical distancing orders are lifted, we will attempt to complete any incomplete study procedures in-person: memory testing with modified MOCA (or the TRAILS and SLUMS tests), as well as the chair stand test required for assessment of frailty in subjects age 55-64.

Aim 2 -

We used the qualitative data from Aim 1 to design a deprescribing quality improvement program (QIP) for dialysis patients. We are seeking IRB approval for evaluation of this deprescribing QIP.

Brief Description of Deprescribing QIP: The dialysis deprescribing team (pharmacist, nurse, physician) will conduct the process of deprescribing in patients aged 55 and older who have been undergoing dialysis for at least 3 months and have regular use of a PIM based on their Duke electronic medical record (EMR). PIMs for deprescribing will include antihypertensive PIMs (alpha blockers and central alpha agonists) and psychoactive medications, such as gabapentinoids, muscle relaxants, and Z-drugs (e.g., zolpidem). The team will also conduct chart review to discern if the patient is a candidate for deprescribing the specific PIM. After identification of eligible patients, the deprescribing team will provide a deprescribing recommendation (including instructions for deprescribing the PIM) to the nephrologist (or other dialysis provider). If a patient agrees to attempt deprescribing a PIM, the team will supervise implementation and monitoring of the deprescribing.

Deprescribing PIMs is considered a best practice for providing care to older adults with multiple comorbidities. It can improve quality of life, reduce medication related problems and lower financial burden to patients.¹ It is consistent with the American Geriatrics Society's guiding principles to make clinical decisions that optimize benefit and minimize harm.² Deprescribing, as part of routine geriatrics care, carries minimal risk. It is not routine for dialysis clinics; however, a Canadian dialysis deprescribing QIP demonstrated favorable preliminary outcomes on reducing polypharmacy.³

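### Aim 2 schedules its only dated check for adverse drug withdrawal events at one month, while the sustainability result is read at three months from a call with no stated safety question

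*Combined protocol and SAP*

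**What the plan says.** The Data & Safety Monitoring section makes ADWEs the leading safety concern of the program that Aim 2 evaluates. It counts both physiological withdrawal and intolerance in the form of worsened symptoms. It sets one dated check, a record review plus contact with each patient one month after deprescribing onset. The Monitoring row of the deprescribing-steps table agrees for both formats: the team will "contact patient after a month to check on progress and ask about symptoms".

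Under Change in PIM burden, the plan adds a later contact: "Participants who agree to deprescribe will be called after 3 months to see if they remain off PIM or at a lower dose". The result is the proportion still off the drug or on less of it, among those who can be reached. The Deprescribing Attempts text describes the same call in the past tense: "participants who agreed to deprescribed were called after 3 months to see if they remained off PIM".

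The Aim 2 list of additional data includes the presence, type and seriousness of ADWEs, but with no time point or window. Data & Safety Monitoring also lets a drug be resumed or raised again whenever deprescribing is not tolerated. The analysis section plans descriptive statistics.

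**The concern.** The plan looks for harm on schedule at month 1 and reads its benefit-side result at month 3. A patient who tolerates the first month, then has worsened symptoms and goes back on the drug, falls between the two. Whether that event reaches the dataset depends on the patient making contact, a clinician recording it, or the team noticing it without a set prompt. These routes need not work equally well across patients, or across two formats that differ in who talks to the patient.

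Two uses of the data are affected. The first is the ADWE summary: without a stated window, a reader cannot tell whether it describes one month or three. The second is the sustainability proportion: a restart caused by an ADWE and a restart for any other reason are different findings for a feasibility study meant to inform a later trial, and the call as described does not separate them.

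**Working it through.** The plan gives no figure to reproduce here, so the check is to set every route by which an ADWE could be recorded beside its timing and content.

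| Route | Section | Fixed time after month 1? | ADWE content stated? |
|---|---|---|---|
| Record review and patient contact | Data & Safety Monitoring; Monitoring row of steps table | No, at one month | Yes |
| Team help with problems while deprescribing | Monitoring row | No, as need arises | Not as a set question |
| Patient-initiated contact | Data & Safety Monitoring | No; described for the time before the one-month check | Yes, once the patient makes contact |
| ADWE and clinical-event items | Additional data for Aim 2 | No date or window | Yes |
| Interviews, 12-15 expected | Patient acceptability | No; only after the decision | Side effects, as part of acceptability |
| Monitoring as in routine practice | Risk/Benefit Assessment | No schedule | In general terms |
| Quarterly review with the Safety Monitor | Data & Safety Monitoring | Scheduled, but reviews ADWEs already found | No new patient check |
| Repeat surveys | Geriatric Assessment | Yes, 3 months from baseline collection, within 2 weeks | No: mood, falls, cognition, function |
| Later call | Change in PIM burden | Yes, 3 months | No: PIM status only |

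Only the last two rows are patient contacts at a fixed time after month 1, and neither has stated ADWE content. The surveys also reach only patients who consent to them. No row combines a fixed later date with an ADWE question.

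**Length of the interval.** The one-month check is dated from onset. The start event of the 3-month call is not spelled out; it could be agreement or onset. Let g be the months from agreement to onset (not stated; assumed range 0 to 1).

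- Call counted from onset: time without a scheduled look = 3 - 1 = 2 months, and 2/3 = 67% of the period. In weeks, 13.0 - 4.3 = 8.7.
- Call counted from agreement: the check falls at 1 + g and the call at 3, so the interval is 2 - g months out of 3 - g since onset. At g = 0 this is 2 of 3 (67%); at g = 0.5, 1.5 of 2.5 (60%); at g = 1, 1 of 2 (50%).

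These are shares of time. They say nothing about how many ADWEs fall in the interval.

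**Denominators.** The one-month contact is meant for each patient. The 3-month result is limited to agreeing patients who are reached. A patient not reached at 3 months therefore contributes neither a PIM status nor a scheduled late safety look, and no 3-month record review is planned to fill the gap.

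**The case against.** The strongest reply is that later events are not ignored. Team help during the deprescribing step carries no one-month limit. The ADWE items are to come from records and from patient communication in the program, and the 3-month call can reasonably be read as such a communication. Interviews cover side effects, routine monitoring continues, and ADWEs that come to light are reviewed at once. All of this stands. It rules out saying that late ADWEs go unrecorded, or that a restart for an ADWE could show up only as a failure to sustain. That outcome is a worst case, reached only if every other route fails. What remains is that none of these routes is scheduled after month 1, and nothing tells the caller to ask.

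A reader might also infer that the one-month check comes before tapers end. The documents do not support this. Taper length is not stated and may be in the PIM-specific protocols that the plan says will be written. The Risk/Benefit Assessment counts events after a reduced dose as well as after removal, so a check during a taper is still informative.

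A third tempting reading is that the baseline surveys are invalid because patients are invited only after deciding: "After a patient decides (either for or against deprescribing), they will receive a recruitment letter". The plan nowhere calls them pre-deprescribing values and names no survey-change outcome. The survey date must be known to time the repeat, and deprescribing is itself recorded: "We will document deprescribing in medical record and to pharmacy". A before/after flag should therefore be derivable. This merits no more than a note to report survey dates relative to the first PIM change.

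Finally, Aim 2 is a small descriptive feasibility evaluation. That limits the consequence to interpretation; no error rate or power is at stake.

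**Conclusion.** The point holds in a limited form. On the text, there is one dated patient-level ADWE check, at one month, and a later call whose only stated purpose is PIM status. Scheduled safety ascertainment therefore stops well before the sustainability result: about two thirds of the period if the call is counted from onset, and half to two thirds over the assumed range for a call counted from agreement. Later ADWEs may still be captured, but unevenly and with no defined window. The documents give no event rate, so the size and direction of any effect on the reported ADWE proportion cannot be derived. The change should be made because it strengthens the safety description at little cost; nothing here shows that the plan's feasibility conclusions would be wrong without it.

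**What to change.** 1. At the planned 3-month call, ask the ADWE items already in the Aim 2 data list, and the reason for any restart or increase of the PIM.
2. Add a chart look-up at 3 months for every patient who started deprescribing, including those not reached by telephone.
3. Record the deprescribing onset date, which is not in the Aim 2 data list. The program's medical-record entry is a ready source, since "the team will supervise implementation and monitoring of the deprescribing". In the Provider Communication Only format, the existing query can carry it too: "We will ask dialysis providers if the patient agreed to deprescribe after a month". State the event from which the 3 months are counted.
4. Report ADWEs over 0-1 and 0-3 months among patients who started, with the numbers started, reached, and assessed by chart only.
5. Handle any event found under the review and reporting procedures already in Data & Safety Monitoring. No clinical management rule changes.

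The cost is one date field, a few call items and one chart look-up per starter. The number of starters is not stated; recruitment from the two formats is capped at 30 patients, who may have decided either way. Any additional ADWEs found add reviews under the existing procedures. For patients already called, only chart recovery is possible, and their results should be labelled as chart only for ADWEs.
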